**Hepatotoxicity:**

Grade 3-4 hepatotoxicity according to CTCAE is defined as an increase in serum bilirubin of >3 times the upper limit of normal (ULN) or aspartate aminotransferase (AST), alanine aminotransferase (ALT), or alkaline phosphatase (AlkPhos) >5 times the ULN. During the dose expansion phase of the trial, this will be managed with temporary discontinuation and subsequent dose adjustment of IRX5183. As soon as the bilirubin, AST, ALT, and/or AlkPhos returns to Grade 2, IRX5183 will be resumed at less than or equal to 50% of the previous dose (e.g. 25 mg for 50 mg or 75 mg dosing, 50 mg for 100 mg dosing) during the first week. Thereafter, in the absence of worsening previous toxicity, IRX5183 will be resumed at full dosing. In the case of reemergence of hepatotoxicity, the drug will be permanently discontinued. These stipulations are based on prior reports that ATRA-induced hepatotoxicity improves with temporary discontinuation of the drug.

**Other non-hematologic toxicities:**

During phase II of the trial, IRX5183 should be dose reduced by 1 dose level for grade 2 non-hematologic toxicity. If the RP2D is DL(-1), this dose will be 25 mg every other day. For grade 3-4 non-hematologic toxicity, therapy will be discontinued until resolution to grade <2 and then restarted at a 2 level dose reduction. If the RP2D is DL(-1), the patient will go to 25 mg every other day since this is the lowest feasible dose. If symptoms recur to a grade 3-4 the patient will be removed from the trial.

**Myelosuppression:**

If the bone marrow at the end of cycle 1 or 2 of therapy is hypoplastic, as defined by less than 5% cellularity, and the patient has grade 4 hematologic toxicity per CTCAE, the patient may have a drug-free window of up to 2 weeks to look for count recovery. Treatment will be re-initiated after this time. For grade 4 hematologic toxicity that is treatment-related and lasts more than 5 weeks, one DL reduction will be recommended. If the patient is on DL(-1), the dose will go to 25 mg every other day. If myelosuppression lasts beyond 7 weeks or persists for 2 consecutive courses, bone marrow aspirate will be collected and assessed for disease progression. In the case of PD, patients will come off study. If the patient has SD or better, they can go back on therapy on the next lower dose than the previous. If the patient was already taking IRX5183 25 mg every other day, they will stop therapy for up to 2 weeks to allow for count recovery prior to resuming the same dose.

The following criteria will be used to determine dose skipping, restarting doses, or discontinuing IRX5183 during the *all phases* of the trial:

**Differentiation syndrome:**

Grade 3-4 toxicities associated differentiation syndrome (unexplained fever, dyspnea, pleural

and/or pericardial effusion, pulmonary infiltrates, renal failure, hypotension, and unexplained weight gain greater than 5 kg) will be treated with dexamethasone 10 mg IV twice daily as per section 5.3.1 above and IRX5183 will be temporarily discontinued until resolution of symptoms to grade 2 or below, while on concomitant steroid therapy. Signs or symptoms of differentiation syndrome that do not return to grade 1 within 2 weeks of steroid therapy will be considered a DLT and the patient will be removed from the trial. If differentiation syndrome subsequently recurs to 3 or above, the patient will also be removed from the trial.

### **Rash:**

Rashes can be common with retinoid therapies. Therefore, there will be no dose modifications for a grade 1-2 rash. Patients with a grade 1-2 rash should be treated with topical steroids. If the patient develops or progresses to a grade 3 rash, then the patient should be started on oral steroids (specific type and dosing to be determined by the treating physician) and the drug should be held for up to 2 weeks until the rash resolves to  $\leq$  grade 2. If the patient develops a grade 4 rash, they should permanently discontinue IRX5183 and come off study.

### **6.2. Discontinuation of IRX5183 for related adverse events:**

Permanently discontinue IRX5183 for any of the following:

- 1) Persistent adverse reaction(s) thought to be due to IRX5183 therapy, which require holding more than 2 weeks of treatment doses.
- 2) Any grade 3 or 4 event (see exceptions in section 5.2 and 6.1 above).
- 3) Severe or life-threatening adverse reactions, including any of the following:
  - Stevens-Johnson syndrome, toxic epidermal necrolysis, or rash complicated by full thickness dermal ulceration, or necrotic, bullous, or hemorrhagic manifestations
  - Respiratory failure non-responsive to steroid therapy
    - ❖ Any adverse event, laboratory abnormality or intercurrent illness, which in the judgment of the investigator presents organ specific injury and/or a substantial clinical risk to the patient with continued dosing.
    - ❖ The following neurological adverse event requires permanent discontinuation of IRX5183 and defines unacceptable neurotoxicity:
      - Any motor neurologic toxicity  $\geq$  grade 3 regardless of causality
      - Any  $\geq$  grade 3 treatment related sensory neurologic toxicity

### **6.3. Exceptions to permanent discontinuation:**

- 1) Potentially reversible inflammation ( $<$  grade 4), attributable to a local anti-tumor reaction and a potential therapeutic response. This includes inflammatory reactions at sites of myeloid sarcoma or in draining lymph nodes.
- 2) Hospitalization for  $\leq$  grade 2 adverse events where the primary reason for hospitalization is to expedite the clinical work-up.
- 3) Patients with the following conditions where in the investigator's opinion continuing study drug administration is justified based on the potential for continued clinical benefit:
  - ❖ Patients with grade 3-4 differentiation syndrome-related symptoms if symptoms resolve within 2 weeks of high-dose dexamethasone therapy.

- ❖ Grade 2 skin rash treated with topical steroids for less than 4 weeks.

## 7. TREATMENT EVALUATION AND TOXICITY MONITORING

### 7.1. Clinical Responses:

All patients initiated on therapy will be evaluable for toxicity. The primary endpoint of clinical efficacy will be evaluated following at least two cycles of therapy. See Section 7.3 for response criteria.

### 7.2. Assessment of Response:

1. Complete blood counts with WBC differential will be measured twice weekly during the first cycle of treatment, at least weekly throughout the second cycle of therapy, at least every other week during consolidation/maintenance, and at least monthly during extended maintenance, or as often as clinically indicated.
2. Blood chemistries will be measured twice weekly during the first cycle of treatment, at least weekly throughout the second cycle of therapy, at least every other week during consolidation/maintenance, and at least monthly during extended maintenance, or as often as clinically indicated.
3. Fasting lipids with triglyceride evaluation will occur q2 weeks through the first month and then q8 weeks subsequently for assessment of toxicity.
4. Bone marrow aspirate and biopsies for clinical assessment (morphologic analysis, cell count/differential, flow cytometry, FISH/cytogenetics for patients with baseline abnormalities, and molecular studies for patients with baseline abnormalities) and biologic correlates (see section 8 below) will be collected at the following time points:
  - ❖ Day 14 ( $\pm$  3 days) of cycle 1 (not required to stay on study)
  - ❖ At the completion of cycle 1
  - ❖ At the completion of cycle 2
  - ❖ At the end of every two cycles of treatment during consolidation/maintenance
  - ❖ After every 4 cycles of treatment during extended maintenance
  - ❖ Drug levels will be obtained in the peripheral blood (PB) and BM with liquid chromatography mass spectroscopy (LCMS), described in detail in section 7.8.
5. PT/PTT will be followed as needed for those patients who are receiving an anticoagulant during protocol therapy.
6. A track of the total number of transfusions required will be kept.
7. Quality of life assessment per the FACTLeu questionnaire (available at <http://www.facit.org/FACITOrg/Questionnaires>) at the completion of the induction and maintenance phases, with the help of the research team.
8. Response to treatment will be assessed after completion of at least 2 cycles. Patients will be categorized based on standard IWG-2003 response criteria for AML (Appendix A1) and IWG-2006 criteria for MDS (Appendix A2-A3) and patients with at least SD will continue on treatment (see section 5.1).
9. All patients will be evaluated for hematologic improvement (HI) per IWG-2006 MDS criteria (Appendix A2).
10. Those showing CR at the completion of consolidation/maintenance will have treatment ceased to assess duration of response (will check biweekly CBC for the first month, then

monthly for at least 6 months, and bimonthly bone marrow assessments for at least 6 months). Patients will be allowed to resume treatment if they relapse during this observation period.

11. If patients continue with SD, HI, or PR after consolidation/maintenance, they will continue onto extended maintenance for up to an additional year.
12. At the end of extended maintenance, patients may be able to continue on therapy, per the discretion of Io Therapeutics and the PI.
13. Time to first response (CR/CRi/PR for AML, CR/CRi/PR/HI for MDS) and time to best response will be tracked for each patient.
14. Time from treatment initiation to progression (as defined per IWG criteria in Appendix A1-A2) will be tracked for each patient.
15. Time from treatment initiation to death will be tracked for each patient.

### **7.3. Measurement of Response / Response Criteria:**

The primary endpoint of clinical response is defined by the International Working Group recommendations (see Appendix A1-A3) for therapeutic trials in AML and MDS and includes CR, complete remission with incomplete count recovery (CRi, formerly known as morphologic leukemia-free state or marrow CR), partial remission (PR), HI, SD, and PD (Cheson et al., 2003). We will also include an assessment of HI per MDS IWG-2006 recommendations as one of our secondary endpoints in our AML patients (see Appendix A2). In addition to the criteria in Appendix A1, the following will be considered as PD:

- 1) A significant increase in bone marrow blasts beyond 4 weeks of starting the drug:
  - a. if baseline 51-100% blasts – an increase of greater than 50% of baseline
  - b. if baseline 26-50% blasts – an increase up to 2 x the baseline
  - c. if baseline 0-25% blasts – an increase up to 3 x the baseline
- 2) A rising peripheral WBC after adequate dosing with hydroxyurea (see section 5.3 above)

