
STUDY DESIGN:
 
This is a single-center open-label prospective phase I/II study with an escalation and expansion phase evaluating the use of CYP26 resistant RAR<math>\alpha</math> specific retinoid IRX5183 in 1) patients with relapsed and/or refractory AML and 2) patients with high-risk MDS or CMML.
 
The treatment scheme is summarized below and the dose escalation of IRX5183 is shown in Table 1. IRX5183 will be administered orally daily on days 1-28 of each cycle for 2 cycles of induction. In the phase I part of the study, there will be 3 dose levels (dose level 1 [DL1] with 50 mg, DL2 with 75 mg, and DL3 with 100 mg), with 1 additional dose level to be only used if excessive toxicity noted at the DL1. There will be no intra-patient dose escalation. In the phase II part of the study, we will use the optimal dose identified in phase I and will aim to recruit a total of 27 patients per a Simon's 2 stage design, using a type I error rate of 0.05, power of 0.8, response probability of poor drug 0.05, and response probability of good drug 0.2. The first stage sample size will be 13 and if we do not reach the pre-specified requirement of at least one response (complete remission [CR] or partial response [PR] for AML or CR or PR or hematologic improvement [HI] for MDS), the trial will be aborted. After induction, all patients who do not experience significant toxicity or disease progression will continue on a consolidation/maintenance phase of the study in which 4 additional 28-day cycles of IRX5183 will be administered. This phase will use the same dose used in the induction phase for each individual patient. Patients achieving CR after consolidation/maintenance will enter an observation phase, with a chance to re-enter the study at relapse, and patients with a PR, HI, or stable disease (SD) after consolidation/maintenance will be able to remain on study for extended maintenance for an additional year. Select patients may be eligible to continue beyond this point per the discretion of Io Therapeutics and the principal investigator (PI).
	

**Table 1: Dose Escalation of oral IRX5183 administration in phase I part of the study.** \*: DL(-1) will only recruit if the maximally administered dose was reached at DL1. DL: dose level.

Dose level (DL)	Daily dose (mg)
DL(-1)*	25
DL1	50
DL2	75
DL3	100

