**Study Phase II:**

The phase II part of the study will use the optimal dose identified in the phase I part of the study and will aim to recruit a total of 27 patients with AML and HR-MDS at the RP2D (see sample size calculation in section 11). The primary goal of the therapy in this phase of the trial is to determine response after receiving at least 2 cycles of therapy per IWG criteria. Analysis of clinical response will take place after the first 13 patients complete induction therapy, and enrollment will continue to the planned 27 patients if the first stage has at least 1 patient achieve a CR or CRi or PR (AML) or CR or PR or HI (MDS). We will halt enrollment after the first 13 patients complete induction therapy until we have their response data. In addition to IWG response, many secondary endpoints will be assessed as outlined in section 11 below.

**Figure 2: IRX5183 Administration Schema.** Induction phase will consist of 56 days of oral IRX5183 daily. Consolidation/maintenance phase will begin once patient has confirmed SD or better and will continue for up to four 28-day cycles. If patient is in CR after consolidation/maintenance, will hold therapy and monitor, and resume therapy if they relapse. If they have SD or better after consolidation/maintenance, they will continue on maintenance therapy for up to 1 additional year. Select patients may be eligible to continue for longer.

**Table 1: Dose Escalation of oral IRX5183 administration in phase I part of the study.** \*: DL(-1) will only recruit if the maximally

administered dose was reached at DL1. DL: dose level.

Dose level (DL)	Daily dose (mg)
DL(-1)*	25
DL1	50
DL2	75
DL3	100

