## 5.2. Definition of dose-limiting toxicity:

For purposes of dose-escalation, dose-limiting toxicity (DLT) will be defined as the occurrence of any of the following during the first 28 days of therapy:

- ❖ Any grade 3 or 4 non-hematologic toxicity with the following exceptions:
  - Transient laboratory abnormalities that can be treated or resolve to grade 2 or less within 1 week from holding study drug.
  - Grade 3-4 non-hematologic toxicities that resolve to  $\leq$  Grade 1 within 1 week of holding study drug
  - Grade 3-4 expected and known drug class-related toxicities associated with differentiation syndrome (see definition below in section 9.2.4) that resolve within 2 weeks of steroid therapy to grade 1 will be excluded as DLT for purposes of dose escalation. This is due to the fact that such events are expected of therapy with retinoids that are effectively causing differentiation. If grade 3 or above differentiation syndrome recurs after this time, it will then be considered a DLT.
  - Asymptomatic Grade 3 hypertriglyceridemia will not be considered a DLT for purposes of dose escalation.
- ❖ Grade 4 hematologic toxicity, including only *treatment-associated* aplasia (to be investigated with a BM test) that persists beyond 4 weeks. Given that severe anemia, neutropenia and thrombocytopenia are features of AML and are commonly encountered in this patient population, they will not be used to define DLT except if associated with prolonged treatment-associated aplasia.
  - If the bone marrow at the end of cycle 1 or 2 of therapy is hypoplastic, as defined by less than 5% cellularity, the patient may have a drug-free window of up to 2 weeks to look for count recovery and treatment will be re-initiated after this time if toxicity returns to  $\leq$  Grade 3

Management and dose modifications associated with the above adverse events are outlined in Section 6.

Toxicities will be assessed during the first cycle of therapy and throughout the trial to make sure there are no late adverse effects. If any chronic toxicity becomes apparent, we will evaluate whether changes in trial design are required.

Dose escalation will proceed within each cohort according to the following scheme.

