## 11. STATISTICAL CONSIDERATIONS

### 11.1. Study design & endpoints:

In the dose-escalation part of the study, there will be 3 dose levels (dose level 1 [DL1] with 50 mg, DL2 with 75 mg, and DL3 with 100 mg), with 1 additional dose level to be only used if excessive toxicity noted at the DL1. There will be no intra-patient dose escalation. Dose-escalation rules are defined through a standard 3+3 algorithm as outlined in Section 5.2.

The phase II expansion part of the study will aim to recruit a total of 27 patients with either R/R-AML or HR-MDS, and there will be an interim analysis after 13 patients for futility through a Simon two-stage minimax design based upon a Type I error rate of 0.05, power of 0.8, response probability of poor drug 0.05, and response probability of good drug of 0.2, based on prior relapsed and refractory AML trials and CTEP data on non-pediatric oncology trials from 2001 to 2012 (Itzykson et al., 2015; Ritchie et al., 2013; Thol et al., 2015; Yoko Korenaga Fukuda, 2014). Stage 1 will enroll 13 patients at the RP2D and will require at least 1 response for

continued enrollment to Stage 2, to reach the total of 27 patients. A total of 4 or more responses out of 27 patients will be considered encouraging evidence for future larger clinical trials of IRX5183.

Response will be defined per IWG criteria as CR, CRi, or PR for AML patients and as CR, CRi, PR, or HI for MDS patients (see definitions in Appendix A) and will be determined with each BM assessment. The composite of these responses across our study population will be referred to as the overall response rate (ORR). Rates of CR, CRi, PR, HI, and the composite endpoint of ORR will be summarized and reported with an exact 95% confidence interval.

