**APPENDIX A1.** Modified International Working Group (IWG)-2003 (A) response criteria, (B) treatment failure, and (C) endpoints in AML.

**A.**

Response Criterion	Time of Assessment	Neutrophils (μL)	Platelets (μL)	Bone Marrow Blasts (%)	Other
Early treatment assessment	7-10 days after therapy	NA	NA	< 5	
Morphologic leukemia-free state	Varies by protocol	NA	NA	< 5	Flow cytometry EMD
Morphologic CR	Varies by protocol	> 1,000	> 100,000	< 5	Transfusion EMD
Cytogenetic CR	Varies by protocol	> 1,000	> 100,000	< 5	Cyogenetics—normal, EMD
Molecular CR	Varies by protocol	> 1,000	> 100,000	< 5	Molecular—negative, EMD
Partial remission	Varies by protocol	> 1,000	> 100,000	> 50 or decrease to 5-25	Blasts < 5% if Auer rod positive

Abbreviations: AML, acute myelogenous leukemia; EMD, extramedullary disease; CR, complete remission.

**B.**

Category	Definition
Resistant disease	Patient survives $\geq$ 7 days post-CT; persistent AML in blood or bone marrow
Aplasia	Patient survives $\geq$ 7 days post-CT; death while cytopenic, with aplastic bone marrow
Indeterminate cause	Patients who die < 7 days posttherapy Patients who die > 7 days posttherapy with no PB blasts, but no bone marrow examination Patients who do not complete the first course of therapy
Morphologic relapse	Reappearance of blasts post-CR in PB or bone marrow
Molecular or cytogenetic relapse	Reappearance of molecular or cytogenetic abnormality

Abbreviations: AML, acute myelogenous leukemia; CT, chemotherapy; PB, peripheral blood; CR, complete remission.

**C.**

Outcome	Response Category	Point of Measurement	Definition
Overall survival	All patients	Entry onto trial	Death from any cause
Relapse-free survival	CR	Leukemia-free state	Disease relapse or patient death from any cause
Event-free survival	All patients*	Entry onto trial	Treatment failure, disease relapse, or patient death from any cause
Remission duration	CR	Date of CR	Disease relapse

NOTE. Complete blood counts should be evaluated at least monthly, or more often if clinically indicated, to establish the durability of responses. Abbreviations: AML, acute myelogenous leukemia; CR, complete remission.

\*Under circumstances where presentation of event-free survival may be appropriate for responders only, this point should be clearly stated.

(Cheson et al., 2003)

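### AML CRi is equated with a leukemia-free marrow that has no count or cellularity requirement, so a hypoplastic marrow handled elsewhere as toxicity can count as a primary response

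*Combined protocol and SAP*

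**What the plan says.** **How CRi is defined.** Section 7.3 is the only place that says what CRi means: "complete remission with incomplete count recovery (CRi, formerly known as morphologic leukemia-free state or marrow CR". Section 7.2 sends AML patients to one table: "Patients will be categorized based on standard IWG-2003 response criteria for AML (Appendix A1". Part A of Appendix A1 has no CRi row, so for AML the applicable row is "Morphologic leukemia-free state". That row gives NA for neutrophils, NA for platelets and marrow blasts below 5%, and lists flow cytometry and extramedullary disease (EMD) under Other. It states no minimum cellularity and no duration.

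**Where CRi counts.** Section 11.1: "Response will be defined per IWG criteria as CR, CRi, or PR for AML patients". These responses feed the rules of at least 1 in 13 and at least 4 in 27. Section 5.1 (Study Phase II) continues enrollment if the first stage has "at least 1 patient achieve a CR or CRi or PR (AML"). The synopsis states the same gate without CRi: "complete remission [CR] or partial response [PR] for AML".

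**How the same marrow is treated elsewhere.** Section 5.2, under grade 4 hematologic toxicity, begins a rule with "If the bone marrow at the end of cycle 1 or 2 of therapy is hypoplastic, as defined by less than 5% cellularity" and allows a drug-free window. Section 6.1 (Myelosuppression) repeats it for patients who also have grade 4 hematologic toxicity. Section 5.1 makes the end of cycle 2 the primary response assessment.

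**The concern.** The name CRi implies some count recovery, but the rule requires none. A marrow emptied by treatment has few cells of any kind and can show blasts below 5% for that reason alone. On that marrow one part of the protocol looks for toxicity and another can record a response. Nothing says which reading prevails:

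- Section 11.8.2 does not make a hypoplastic marrow unevaluable.
- Part B of Appendix A1 classes aplasia as treatment failure only when the patient dies while cytopenic.

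The stated hypothesis is better hematologic parameters and/or fewer marrow blasts, through differentiation. An empty marrow meets the blast limb without showing differentiation. Because the thresholds are only 1 and 4 responses, a single such marrow carries weight in both decisions.

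The point is confined to AML. The MDS marrow CR row in Appendix A2 also lacks a count floor, but it requires at least a 50% fall in blasts, and responses in that table must last at least 4 weeks.

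**Working it through.** **1. Reproduce the design.** Inputs from Section 11.1: n1 = 13, continue if at least 1 response; N = 27, positive if at least 4; p0 = 0.05, p1 = 0.20.

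P(success) = Σ over x ≥ 1 of P(X1 = x; 13, p) × P(X2 ≥ 4 − x; 14, p).

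At p = 0.05:

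| Stage 1 responses | P(X1) | P(enough in the next 14) | Product |
|---|---|---|---|
| 1 | 0.3512 | 0.0301 | 0.0106 |
| 2 | 0.1109 | 0.1530 | 0.0170 |
| 3 | 0.0214 | 0.5123 | 0.0110 |
| 4 or more | 0.0031 | 1 | 0.0031 |

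The sum is 0.0416. At p = 0.20 the same formula gives 0.801. The chance of passing stage 1 at the null is 1 − 0.95^13 = 0.487. A search over all two-stage designs confirms 27 as the smallest feasible N, so the stated minimax design reproduces.

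**2. One hypoplastic marrow counted, with no assumed rate.** Suppose one of the first 13 is scored CRi on such a marrow and the other 26 patients respond at 5%. Under Sections 5.1 and 11.1 the gate is passed with certainty. Success then needs at least 3 of 26:

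1 − (0.2635 + 0.3606 + 0.2372) = 0.139.

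That is 0.139 / 0.0416 = 3.3 times the design's type I error. It is conditional on the event having happened.

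**3. Sensitivity to an assumed rate.** The documents give neither an aplasia rate nor an AML share, so both are assumptions. Let q be the proportion of true non-responding AML patients with a hypoplastic marrow that meets the leukemia-free row, and f the AML share. Only non-responders can be misclassified, so the counted rate is p = 0.05 + 0.95 × q × f, put into the formula of step 1.

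| q | p, f = 0.5 | False success, f = 0.5 | p, f = 1 | False success, f = 1 |
|---|---|---|---|---|
| 0 | 0.0500 | 4.2% | 0.0500 | 4.2% |
| 0.5% | 0.0524 | 4.8% | 0.0548 | 5.5% |
| 1% | 0.0548 | 5.5% | 0.0595 | 7.0% |
| 2% | 0.0595 | 7.0% | 0.0690 | 10.7% |
| 5% | 0.0738 | 12.8% | 0.0975 | 25.6% |

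The nominal 5% is exceeded at q = 1% with half AML and at q = 0.5% with all AML.

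**4. The gate depends on the page followed.** Under Sections 5.1 and 11.1, one such marrow passes stage 1. Under the synopsis it does not, yet if stage 1 is passed on another response it still counts toward 4 of 27 under Section 11.1.

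**The case against.** - **The row asks for more than a blast count.** This stands. Flow cytometry and EMD are listed, and the patient must have received 2 cycles and been re-evaluated. A reader might infer that every aplastic marrow scores as a response; the text supports only that one can.
- **Section 7.2 invokes the standard IWG-2003 criteria, which may carry a marrow-adequacy rule.** That cannot be checked from these documents. Appendix A1, the table to be applied, reproduces none.
- **Toxicity and response are separate labels, and one patient may have both.** This is true, and the sections serve different purposes: the window in 6.1 needs hypoplasia with grade 4 hematologic toxicity, and the aplasia DLT in 5.2 needs persistence beyond 4 weeks. Counting leukemia-free state in the response rate is partly an endpoint choice. But the plan labels it incomplete count recovery, and no section says how an empty marrow is read for response.
- **The event may be rare.** This also stands. The only hematologic effect listed from the earlier phase I trial (Section 9.2.1) is anemia, and Section 2.5 gives that trial's DLTs as alkaline phosphatase elevation and mucosal inflammation. Still, the protocol writes aplasia into its DLT and dosing rules, so it regards the event as foreseeable.
- **CRi will be visible.** Section 11.1 reports CR, CRi, PR and HI separately with exact intervals, and a positive result only supports larger trials. That helps interpretation afterwards, but the go/no-go counts still use the composite.

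**Conclusion.** The concern holds as a definitional fault in the primary endpoint. As written, a hypoplastic end-of-cycle-2 marrow can count as an AML response toward 4 of 27. It can also count toward 1 of 13 under Sections 5.1 and 11.1, but not under the synopsis.

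The size that needs no assumed rate is conditional: one such marrow among the first 13, with the other 26 at 5%, takes the chance of declaring success from 4.2% to 13.9%. The rate-based figures, 4.8% to 12.8% with half AML and 5.5% to 25.6% with all AML, rest wholly on assumed q of 0.5% to 5% and an assumed AML share. They also suppose that the 5% benchmark excludes such marrows, which the documents do not settle.

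A reader might infer that the trial's type I error is in fact several times nominal. The documents do not support that, because they give no aplasia rate and at low rates the excess is small. What they support is that the rule permits the misclassification and that the thresholds are low enough for one case to matter.

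**What to change.** 1. In Appendix A1, Section 7.3 and Section 11.1, define AML CRi separately from leukemia-free state.
2. State that a marrow meeting the protocol's own definition of hypoplasia (under 5% cellularity) is not scored as a response at that assessment. For the 1-of-13 gate it counts as a non-response unless a later scheduled marrow and counts show response, so the stage 1 readout does not wait. This matters because enrollment is halted for that readout and the next scheduled marrow comes after cycle 4.
3. Report leukemia-free state without any count recovery as its own category, with the count criterion pre-specified by the sponsor.
4. Reconcile the AML response list across the synopsis, Section 5.1 and Section 11.1.

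This should be settled before the stage 1 marrows are read.

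**Cost.** It takes a table row and matching text in the sections named. A few leukemia-free marrows no longer count as responses, and a late recovery may be missed at the stage 1 gate. Sample size, dosing, toxicity management and the biopsy schedule do not change.
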